A Validation of the Assisted Fluid Management Feature

CLINICAL STUDY PROTOCOL

Medical Device: EV1000 Platform with Acumen[™] Assisted Fluid Management Feature

Date: October 25, 2018

NCT03469570

Title:	A Validation of the Acumen [™] Assisted Fluid Management (AFM)
Short Title:	AFM Study
Purpose:	The primary objective of this study is to evaluate the performance of the Acumen TM Assisted Fluid Management (AFM) Feature in its ability to predict a subject's fluid responsiveness. The validity of the fluid bolus recommendation will be analyzed by reporting the number of recommendations followed by delivered boluses that did and did not have a stroke volume response meeting the set fluid strategy.
	Subjects enrolled in the validation study will have their fluid management decisions guided by the AFM Feature. The decision to provide fluid as recommended by the AFM Feature lies solely with the treating investigator. When a fluid recommendation is made by the AFM Feature, the investigator will assess the subject holistically prior to accepting or declining the system recommendation.
Device Name:	Edwards Lifesciences Acumen [™] Assisted Fluid Management (AFM) software
Overall Design:	Pragmatic, multi-site, clinical study with subjects allocated to a single arm
Sample Size:	330 Subjects
Number of Sites:	Up to 20 sites
Subject Participation:	 Subject participation will include: Screening / consent Placement of arterial line and use of Edwards FloTrac IQ Undergo planned surgical procedure Fluid management during surgical procedure Data Collection Device related adverse event/serious adverse event data collection, if applicable
	Anti-instant to lost (months

Enrollment Period: Anticipated to last 6 months

	Inclusion Criteria:
	1. Be \geq 18 years of age
	2. Non-cardiac/Non-thoracic surgery (e.g., abdominal surgery, combined abdominal/pelvic surgery, major peripheral vascular surgery) expected to last >2 hours post anesthesia induction
	3. Procedure will require Mechanical ventilation
	4. American Society of Anesthesiology (ASA) Score 3 or 4
	5. Expected arterial line placement for surgical procedure and general anesthesia
	6. Projected to receive hemodynamic monitoring during surgical procedure
	 Participate or have authorized representative participate in the Informed Consent process and sign/date the IRB approved informed consent form
	Exclusion Criteria
	8. Are < 18 years of age
	9. Have a body mass index \geq 35 kg/m ²

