## Statistical Analysis Plan (SAP)

Data will be summarized using standard frequentist methods as appropriate per data type, i.e. frequencies (percentages) for categorical data, means, medians, measures of dispersion for continuous data and will be reported overall and by group. Any AE's will also be listed and summarized by site and group. All of the primary analysis will be on the intent to treat (ITT) population. Histograms and boxplots will be used to check distributions and for possible outliers for continuous variables. Mathematical transformations will be applied where appropriate in order to render the continuous variables to a normal distribution. Even if consistency with a normal distribution is found, all descriptive statistics will be reported with 97.5% confidence intervals, estimated from both bootstrapped and traditional estimation methods. Similarly, if not a normal distribution (i.e. proportion, etc.) then the point estimate and one-sided 97.5% confidence interval for the primary effectiveness endpoint recommended at the event level will also be computed using a bootstrap methodology and traditional estimation methods. Following the suggestions of Samuelson and Petrick (2006) a minimum threshold of 4000 bootstrap iterations is recommended for an alpha=0.025.

This approach is recommended for non-Gaussian distributions since it can accommodate correlated data. Any bootstrapping will follow procedure as discussed by Davison, AC and Hinkley, DV (1997). All statistical analysis will be conducted using SAS v9.4 or higher (Cary, NC) or NCSS v11 or higher (Kaysville, Utah, 2016) where specified.

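### The traditional version of the event-level primary interval has no visible allowance for several boluses from one subject, and may cover less than 97.5% if it treats boluses as independent

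*SAP*

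**What the plan says.** The protocol synopsis (Purpose) describes the analysis as "reporting the number of recommendations followed by delivered boluses that did and did not have a stroke volume response meeting the set fluid strategy". The counted unit is therefore a recommendation followed by a delivered bolus, while the enrolled unit is the subject (330, single arm).

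The first paragraph of the SAP says that a "confidence interval for the primary effectiveness endpoint recommended at the event level will also be computed using a bootstrap methodology and traditional estimation methods". The level is one-sided 97.5%, and the traditional methods are not named. It adds that "a minimum threshold of 4000 bootstrap iterations is recommended for an alpha=0.025". This fixes the number of resamples but not what is resampled.

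The second paragraph opens with: "This approach is recommended for non-Gaussian distributions since it can accommodate correlated data". This sentence follows the one on bootstrap iterations and precedes the one on bootstrap procedure, so it most naturally refers to the bootstrap.

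No count of boluses per subject is visible. That subjects contribute several is an inference from two places in the synopsis: "Subjects enrolled in the validation study will have their fluid management decisions guided by the AFM Feature" (Purpose), and surgery "expected to last >2 hours post anesthesia induction" (inclusion criterion 2).

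**The concern.** Boluses given to the same patient share that patient's physiology, ventilation and anaesthetic, so their responses may resemble each other. Where they do, the proportion of responding boluses is less precise than the number of boluses suggests. A standard binomial interval would miss this. So would a bootstrap that draws single boluses.

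The SAP recognises correlation and answers it with the bootstrap. It gives no matching answer for the traditional interval, and the visible text does not say which interval governs if the two differ. This is the only interval the visible SAP specifies for the primary effectiveness endpoint. What is at stake is whether an interval labelled 97.5% has that coverage.

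**Working it through.** **Inputs from the documents.** One-sided 97.5% interval and alpha 0.025 (SAP); 330 subjects (synopsis).

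**Assumed, because the documents do not give them.** Boluses per subject m, mean 2 to 6; within-subject ICC 0.05 to 0.30; response rate p = 0.65; a lower bound, since the SAP gives no direction.

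**The plan's own figure.** 1 − 0.975 = 0.025, so level and alpha agree, with z = 1.960. The sample size of 330 cannot be reproduced: no response rate, performance goal, power, bolus count or correlation is visible.

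**Formulas.**
- Design effect, equal m: DE = 1 + (m − 1) × ICC.
- Design effect, varying m: DE = 1 + (E[m²]/E[m] − 1) × ICC. With m = 1 + Poisson and mean μ, E[m²]/E[m] = (μ − 1 + μ²)/μ, which is 2.50, 4.75 and 6.83 at μ = 2, 4 and 6.
- Coverage of an independent-events bound: Φ(1.960/√DE).
- Shift of the bound when clustering is respected: 1.960 × √(p(1 − p)/(330μ)) × (√DE − 1).

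**Middle case, varying m (μ = 4, ICC 0.2).** DE = 1 + 3.75 × 0.2 = 1.75. Coverage = Φ(1.960/1.323) = 93.1%, an error of 6.92% instead of 2.5%. The independent-events standard error is √(0.2275/1320) = 0.01313. The bound is 0.65 − 1.960 × 0.01313 = 0.6243 under independence and 0.6160 with clustering, a shift of 0.83 points.

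**Closed form across the range.**

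| Mean m, ICC | DE equal / varying m | One-sided error equal / varying | Shift in points equal / varying |
|---|---|---|---|
| 2, 0.05 | 1.05 / 1.075 | 2.79% / 2.94% | 0.09 / 0.13 |
| 4, 0.20 | 1.60 / 1.75 | 6.06% / 6.92% | 0.68 / 0.83 |
| 6, 0.30 | 2.50 / 2.75 | 10.76% / 11.86% | 1.22 / 1.38 |

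Over p = 0.50 to 0.80 the shift runs from 0.08 to 1.28 points (equal m) and from 0.11 to 1.45 (varying m).

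**Simulation check** (beta-binomial, 330 subjects, p = 0.65, varying m).

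| Mean m, ICC | Exact binomial coverage | Subject cluster-robust coverage |
|---|---|---|
| 2, 0.05 | 97.1% to 97.4% | 96.9% to 97.1% |
| 4, 0.20 | 93.4% | 97.1% |
| 6, 0.30 | 88.3% | 97.1% |

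At m = 2 and ICC 0.05 the first row spans repeated runs; with equal m the exact interval covers 97.5%. The exact interval is slightly conservative, which offsets weak clustering, so there is no material loss there. At ICC = 0 the exact interval covers 97.5% to 97.9% and the cluster-robust one 97.2% to 97.4%, with bounds within 0.14 points of each other.

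**Bootstrap** (4,000 resamples, p = 0.6, equal m). Resampling boluses covers 96.5% at m = 3, ICC 0.1 and 93.1% at m = 5, ICC 0.2. Resampling subjects covers 97.6% and 97.7%.

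**The case against.** The strongest reply is that the documents show an unnamed method, not an error. Traditional methods could include a cluster-adjusted estimator. Undercoverage needs three things, none stated: the method ignores clustering, subjects contribute several boluses, and the correlation is positive. The textual support for several boluses is modest, because the plural decisions go with a plural subject. Also, "The decision to provide fluid as recommended by the AFM Feature lies solely with the treating investigator", so some subjects may receive no recommended bolus, whereas the varying-m model gives everyone at least one. All this stands, and it is why the point is conditional and its size assumed.

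Second, the plan already intends an interval that accommodates correlation. This also stands. For the bootstrap, naming the resampling unit only clarifies the stated aim. It does not dispose of the traditional interval, which is planned alongside with no visible adjustment and no rule on which one governs.

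Third, part of the SAP was not available, and the bootstrap procedure is given by a reference that was not seen. Either may settle the matter.

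Fourth, the remedy is not better everywhere. With little or no correlation the cluster-robust bound covers slightly less than the exact one. The gap is a few tenths of a point, against a loss of about 4 to 9 points for the exact bound in the middle and upper cases.

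A reader might also infer that clustering by site must be handled, since treating investigators decide which boluses are given at up to 20 sites. That would rest on an assumed site correlation for which the documents give no basis, so it is not part of this point.

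**Conclusion.** The point holds in conditional form. If the traditional interval treats boluses as independent and within-subject correlation is positive, its coverage tends to fall below 97.5%. Under the assumed values the loss runs from nothing material (mean 2 boluses, ICC 0.05) through about 93% coverage (4, 0.2) to about 88% (6, 0.3). Subject clustering restores about 97% throughout.

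Two stronger readings are tempting and unsupported. One is that the SAP overlooks correlation: it names it and offers the bootstrap for it. The other is that the trial's conclusion would change: no performance goal is visible, so only the accuracy of the stated precision is shown to be affected. The change is worth making because it carries out the SAP's own aim at almost no cost. Confidence is moderate, given the unseen text and the assumed inputs.

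**What to change.** Add to the SAP, where the primary interval is described:

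- The bootstrap resamples subjects with replacement and keeps all boluses of each sampled subject.
- The traditional interval uses a subject-level cluster-robust variance, for example GEE, a ratio estimator or Rao-Scott.
- If intervals differ, a subject-clustered interval is the one relied on, with the bootstrap or the robust-variance version named in advance. An independent-events interval may be shown only as a secondary description.

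If SAP text not seen here already says this, a cross-reference is enough.

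The cost is three sentences and a few lines of code, with no extra subjects or data. Compared with an independent-events bound, the reported bound is about 0.1 to 1.4 percentage points less favourable under the assumed correlation, and within 0.14 points if correlation is zero.
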